Subjects may continue on study drug for up to 28 days if clinically indicated. Per the investigator's discretion, if the subject is treated with Remodulin beyond Day 28, Day 28 will be considered as the last day of study drug administration. These subjects will continue to be followed in the study until they have reached Day 56 (4 weeks after last dose of study drug) or have been discharged from the hospital, whichever comes first.

6.1.4 *Dose Weaning*

Abrupt cessation of study drug will be avoided due to the risk of rebound pulmonary hypertension. Inhaled NO should be weaned and discontinued prior to initiating weaning of study drug. When the subject has reached the treatment goal and is ready to start weaning, the dose of study drug will be held constant at the same dose for at least 12 hours prior to initiating down titration. It is recommended the dose of study drug be decreased by no more than 10ng/kg/min per day either in the same incremental manner as the dose was increased or as determined by the Investigator. Dose decreases in increments greater than 5ng/kg/min are recommended to be avoided, but faster weaning may occur if required per subject care.

If withdrawal from study drug is warranted, the dose of study drug will be weaned until discontinued.

6.1.5 *Initiation of ECMO*

Subjects randomized to study drug may continue to receive study drug during ECMO at the pre-ECMO dose. Subjects should not be unblinded upon initiation of ECMO, unless required for purposes of medically managing the subject. At the conclusion of ECMO, weaning of study drug can begin per the Investigator's discretion.

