10.3.2 Secondary Endpoints

Secondary endpoints (change in OI, P/F ratio, and pre- and post-ductal SpO₂, time on mechanical ventilation, and change in NT-proBNP) will be summarized and tested using group t-test. Kaplan-Meier estimate will be provided for time to event variables (time to discontinuation of iNO, time to initiation of ECMO, and time to clinical worsening) and log-rank test will be used to test the treatment differences.

Plasma samples will be analyzed for treprostinil using a validated bioanalytical plasma assay. Individual and mean treprostinil plasma concentration data, and treprostinil pharmacokinetic parameters, determined as able, will be summarized using descriptive statistics.

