2.1 PRIMARY ENDPOINT

The primary endpoint is the composite endpoint of clinical worsening through Day 14 as defined by one of the following:

- Death
- Initiation of extracorporeal mechanical oxygenation (ECMO) per institutional policies
- Need for additional treatment (initiation of an additional targeted pulmonary vasodilator therapy [eg, phosphodiesterase type 5 inhibitor {PDE-5I}, endothelin receptor antagonist {ERA}, prostanoid, L-citrulline}]

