8.5.3 Time to Event and Censor Status

Time to event and censor status will be calculated based on the rules in Table 8-1 for time to clinical worsening, time to initiation of ECMO, and time to discontinuation of iNO.

Table 8-1 Time to Event and Censor Status Rules

Parameter	Scenario	Formula	Censor Status
Time to Clinical Worsening (days)	Subject with clinical worsening or subject died between Baseline and Day 14	= minimum of (Worsening date, death date) - Randomization date	0 (event)
	Subject without clinical worsening between Baseline and Day 14	= minimum of (Last assessment date - Randomization date, 14)	1 (censored)
Time to initiation of ECMO (days)	Subject initiated ECMO between Baseline and Day 14	= Initiation date - Randomization date	0 (event)
	Subject did not initiate ECMO between Baseline and Day 14	= minimum of (Last assessment date - Randomization date, 14)	1 (censored)
Time to discontinuation of iNO (days)	Subject discontinued iNO between Baseline and Day 14	= iNO discontinuation date - Randomization date	0 (event)
	Subject did not discontinue iNO between Baseline and Day 14	= minimum of (Last assessment date - Randomization date, 14)	1 (censored)

ECMO, extracorporeal mechanical oxygenation; iNO, inhaled nitric oxide

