10.2.5 Time to Clinical Worsening

Data on the clinical worsening assessment page of the eCRF will be used to determine clinical worsening status. Clinical worsening events including the date (study day) of the event and details of the clinical worsening event will be listed. The time to clinical worsening will be calculated according to the rules specified in [Table 8-1](#).

Time to clinical worsening will be summarized by treatment group using product-limit estimates calculated by the Kaplan-Meier method, and displayed graphically as Kaplan-Meier curves. A tabular summary of this analysis will include the number of subjects at risk (sample size), estimated median duration, and a 95% confidence interval for the median duration for each treatment group. The log-rank test will be used to calculate the p-value for treatment differences.

The SAS Procedure LIFETEST will be used. The pseudo SAS statements are listed below:

```
proc lifetest;
  time TimeToWorsening*Censor_Status(1);
  strata Treatment;
run;
```

In addition, the Cox proportional hazards model will be fit to obtain the hazard ratio. The model will include treatment as an explanatory variable. The SAS procedure PHREG will be used.

The pseudo SAS statements are listed below:

```
proc phreg;
  Model TimeToWorsening*Censor_Status(1) = treatment
    / risklimits alpha=0.05 ties=efron;
run;
```

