10.2.7 Time to Discontinuation of iNO

Time to discontinuation of iNO will be analyzed as described in Section 10.2.5.

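### SAP Table 8-1 sets no condition that iNO stays off, so an infant back on iNO at Day 14 can be scored as having discontinued it

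*SAP*

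**What the plan says.** Table 8-1 in SAP section 8.5.3 has two rows for this endpoint. The event row is "Subject discontinued iNO between Baseline and Day 14", timed as "iNO discontinuation date - Randomization date". The censored row is "Subject did not discontinue iNO between Baseline and Day 14", with time taken as the earlier of the last assessment and 14 days.

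SAP 10.2.7 adds only that "Time to discontinuation of iNO will be analyzed as described in Section 10.2.5". That section brings in Kaplan-Meier estimates, the median with its confidence interval, a Cox hazard ratio and the log-rank test ("The log-rank test will be used to calculate the p-value for treatment differences"). Protocol 10.3.2 also names Kaplan-Meier and log-rank for this endpoint and does not define discontinuation.

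Neither document mentions restarting iNO, sets a minimum time off it, or chooses between first and final stop. Protocol 6.1.4 gives the order of weaning: "Inhaled NO should be weaned and discontinued prior to initiating weaning of study drug". The synopsis has time on iNO recorded, and SAP 15.2 plans a Nitric Oxide listing (16.2.6.6). The table list in SAP 15.1 contains no count of restarts and no summary of total iNO time.

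**The concern.** The two rows cover every infant. An infant who stops on Day 3, restarts and is still on iNO at Day 14 did stop within the window, so by its wording that infant belongs in the event row and cannot belong in the censored row. Successful and failed weans are then counted together.

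No other planned summary isolates the restart. The vasodilator component of the primary endpoint is "initiation of an additional targeted pulmonary vasodilator therapy". Its examples do not include iNO, which Protocol 4.3.1 makes background therapy for every infant before randomisation. A restart alone therefore need not count as clinical worsening.

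The order of weaning makes the gap relevant here. When iNO is stopped, study drug is normally still running, so one arm has a pulmonary vasodilator in place and the other has placebo. Whether the stop holds is one place where a treatment difference could plausibly appear, and a first-stop date carries no information on it.

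**Working it through.** **Figures in the plan.** None exist for this endpoint: no restart rate, hazard ratio, expected number of events or power. The arm size comes from the primary endpoint (SAP section 5: 60% versus 30%, one-sided 0.05, at least 80% power). With pooled variance under the null and no continuity correction:

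n = [1.645 × √(2 × 0.45 × 0.55) + 0.842 × √(0.24 + 0.21)]² / 0.30² = (1.157 + 0.565)² / 0.09 ≈ 32.9, so 33 per arm and 66 in total, with power 80.06%.

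The plan's 66 is reproduced, and it does not depend on the iNO rule.

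**What each reading does with the Day 3 infant (restarts, on iNO at Day 14).**
- First stop: event at Day 3.
- Last stop inside the window: still an event. The date may move but the row does not.
- One final-stop date, falling after Day 14: a programmer might censor at Day 14. That would be the programmer's choice, because no text in the SAP directs it.

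**Illustration of size.** All rates below are assumptions.
- 33 per arm, 1,500 simulated trials per scenario, two-sided 0.05 (the SAP section 8 default), times in whole days, censoring at Day 14.
- First-stop times are exponential and identical in both arms, with 60% or 80% stopping by Day 14. The daily hazard is −ln(1 − 0.6)/14 = 0.065 or −ln(1 − 0.8)/14 = 0.115.
- Restart risk is 10% on Remodulin and 10% to 40% on placebo. A restart adds one day on iNO and then the same stopping hazard.
- ECMO and death are not modelled.

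The last column is (share with a first stop by Day 14 − share with a final stop by Day 14) × 33. These are the infants per arm who stopped but are on iNO at Day 14.

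| First stop by Day 14 | Restart, placebo / Remodulin | Log-rank rejects, first stop | Log-rank rejects, final stop | Infants per arm back on iNO at Day 14, placebo / Remodulin |
|---|---|---|---|---|
| 60% | 10% / 10% | 4.9% | 4.5% | 1.3 / 1.3 |
| 60% | 20% / 10% | 3.8% | 5.9% | 2.6 / 1.3 |
| 60% | 30% / 10% | 6.3% | 11.3% | 4.0 / 1.3 |
| 60% | 40% / 10% | 5.0% | 17.1% | 5.2 / 1.3 |
| 80% | 10% / 10% | 5.4% | 5.1% | 1.2 / 1.2 |
| 80% | 20% / 10% | 5.7% | 6.9% | 2.5 / 1.3 |
| 80% | 30% / 10% | 5.1% | 12.1% | 3.8 / 1.2 |
| 80% | 40% / 10% | 5.7% | 21.8% | 5.0 / 1.2 |

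Example for the last column (60%, 40% / 10%): placebo (0.599 − 0.441) × 33 = 5.2; Remodulin (0.599 − 0.559) × 33 = 1.3.

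The simulation standard error is about √(0.05 × 0.95/1500) = 0.6 percentage points near 5%, so the first-stop column shows no more than chance variation around 5%. That result is built in, because first-stop times were set equal.

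**The case against.** A reader might infer that Table 8-1 states a wrong rule, namely that a stop counts even when iNO is restarted. It does not say so. The table is silent, and a brief pause need not be called a discontinuation: for study drug, Protocol 15.1 separates interruption from withdrawal. That defence is weak, because it concerns study drug, and SAP 12.2 adds the word permanent where permanence is meant. The silence still leaves the literal reading in place.

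A reader might also infer that an effect of treprostinil on rebound is being hidden. The documents do not support this. They mention rebound only for stopping study drug (Protocol 6.1.4 and 8.1), never for stopping iNO, and they give no restart rate or expected difference between arms.

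Other data would show part of a failed wean. Death, ECMO or an added vasodilator by Day 14 is a primary event, and the list of vasodilators is illustrative rather than closed. OI is analysed to Day 14, and disease-related events such as hypoxia are summarised by arm. This stands, but none of it counts restarts.

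The strongest objection is size. At 20% versus 10% restarts the final-stop test rejects in only 6-7% of trials, and even at 40% versus 10% it usually misses the difference. Under SAP 8.4 the endpoint is exploratory and tested only if the primary is significant. This also stands, and it limits how serious the gap is.

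Finally, a sustained-stop rule dates an early event using later information. That is true, but the window is short and the rule can be stated in advance.

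**Conclusion.** The event is incompletely defined, and its literal reading scores as weaned an infant who is back on iNO at Day 14. The main harm is to interpretation: in the scenarios above, about 1 to 5 infants per arm would appear on the curve, and in the median and hazard ratio, as off iNO while receiving it.

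The loss of power is modest and conditional. On a first-stop reading, rejection stays near 5%. On final stop it is 11-12% at 30% versus 10% restarts and 17-22% at 40% versus 10%, and there is no difference if restart rates are equal. These figures rest on assumed restart rates, equal first-stop times in both arms and 33 infants per arm.

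The primary analysis and sample size are not affected. The change is worth making because it is cheap and removes a choice that would otherwise fall to the programmer.

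**What to change.** Before unblinding, amend Table 8-1 as follows.

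1. Define the event as sustained discontinuation, dated at the last iNO stop with no restart through Day 14, or through the last assessment if that is earlier. No minimum iNO-free interval is needed, since it would matter only for stops close to Day 14.
2. Censor at Day 14 any infant on iNO at that time.
3. State that an iNO stop at ECMO initiation or death is not a successful discontinuation, and give the censoring time for such infants. The present rows leave this open, and a sustained-stop rule alone would still count an infant taken off iNO at ECMO as a success.
4. Add a table of the number of infants with an iNO restart, by arm.

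The cost is SAP wording and programming. Event times become slightly later and events fewer. The iNO eCRF page must hold start and stop dates for every episode; listing 16.2.6.6 is planned, but its content is not shown, so this needs to be confirmed first.

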8.6 ASSESSMENT WINDOWS

For some assessments, target study day and time have been specified in the protocol. These scheduled assessments, as recorded on the eCRFs, and the corresponding target days and times and study days and time intervals are specified in [Table 8-2](#).

Table 8-2 Assessment Windows for Scheduled Assessments

Visit	Target Study Day/Time	Study Day/Time Interval
Echocardiograms:		
Day 7	Day 7	2 ≤ Study Day ≤ 9
Day 14	Day 14	10 ≤ Study Day
Vital signs, OI, FiO₂, Blood Gas/Lactate:		
Hour 6	Day 1/6 hours	1 ≤ Study Day 1, Hour 6 ≤ 9
Hour 12	Day 1/12 hours	10 ≤ Study Day 1, Hour 12 ≤ 15
Hour 18	Day 1/18 hours	16 ≤ Study Day 1, Hour 18 ≤ 21
Hour 24	Day 1/24 hours	22 ≤ Study Day 1, Hour 24 ≤ 27
Hour 30	Day 2/6 hours	28 ≤ Study Day 2, Hour 6 ≤ 33

Visit	Target Study Day/Time	Study Day/Time Interval
Hour 36	Day 2/12 hours	34 ≤ Study Day 2, Hour 12 ≤ 39
Hour 42	Day 2/18 hours	40 ≤ Study Day 2, Hour 18 ≤ 45
Hour 48	Day 2/24 hours	46 ≤ Study Day 2, Hour 24 ≤ 51
Hour 54	Day 3/6 hours	52 ≤ Study Day 3, Hour 6 ≤ 57
Hour 60	Day 3/12 hours	58 ≤ Study Day 3, Hour 12 ≤ 63
Hour 66	Day 3/18 hours	64 ≤ Study Day 3, Hour 18 ≤ 69
Hour 72	Day 3/24 hours	70 ≤ Study Day 3, Hour 24
PK Assessments		
After 24 hours of study drug dosing	Day 1	24 hours ± 12 hours

Abbreviations: FiO₂, fraction of inspired oxygen; OI, oxygenation index; PK, pharmacokinetic(s)

Note: Study Day = (Assessment Date) - (First Dosing Date) +1

For assessments that are not listed in [Table 8-2](#), the nominal assessment name recorded in the eCRF will be used.

Multiple Evaluations Within the Same Analysis Window

After all the observations have been slotted based on the specifications above, if there are multiple valid observations for an assessment within an assigned analysis visit window, only 1 of these observations will be used for summary statistics and analyses. The observation to be used is determined using the following hierarchy (in decreasing order):

- The observation closest to the target study day and time
- The later observation if 2 observations are equally close to the target study day and time

For missing values where the LOCF algorithm is applied, it is always the last valid observation on treatment carried forward, even though this might not be the observation obtained by the above hierarchy and used in the summaries by visit window.

9 STUDY POPULATION

Unless otherwise specified, all efficacy analyses will be performed on the ITT population, all safety analyses will be based on the Safety population, and all PK analyses will be carried out based on the PK population. In the ITT population, the treatment assignment is based on the assignment upon randomization. In the Safety population, the treatment assignment is based on

the actual treatment the subject received. The PK population will be comprised of those subjects with PK data.

The comparability between the 2 treatment groups will be checked for demographic and baseline characteristics. The p-values from Fisher's exact test (for discrete variables) or Group t-test or Wilcoxon rank sum test (for continuous variables) will be included on summaries but are not intended to be used to test formal hypotheses. For these comparisons, missing or unknown values will be excluded from the calculations.

9.1 SUBJECT ACCOUNTABILITY

All subjects' disposition information will be listed, including the study population the subjects belong to, premature study drug discontinuation status, reason for premature study drug discontinuation, premature study discontinuation status, and primary reason for premature study discontinuation.

The listing of subject accountability will include dates of informed consent, randomization, first study drug dose, each study drug dose change, last study drug dose, and last assessment. Each of these assessments will be summarized by treatment group and overall.

Information regarding whether each subject is included in each analysis population will be listed. If a subject is not included in an analysis population, the reason for exclusion will be noted on the listing. Also noted on the listing will be the randomized treatment assignment and the actual treatment received. The summary will include the frequency and percentage of all subjects in each analysis population as well as summaries for reason for exclusion.

Status of the treatment blind and, if broken, date/time of blind broken and reason will be listed.

9.2 PROTOCOL DEVIATIONS

The status of the entry criteria will be listed for all subjects. The listing will include the date of the initial screening assessment and a list of any specific entry criteria not met. This listing will also include the protocol version that the subject was enrolled under. Entry criteria violations will be summarized by treatment group and overall.

Additional protocol deviations will be documented throughout the study. Protocol deviations will be listed, including the date of the deviation, the type of deviation, and the severity of the deviation. The protocol deviations will also be summarized by treatment group and overall.

9.3 OTHER DESCRIPTIONS OF STUDY POPULATION

9.3.1 Demographics

All demographic data will be listed for all subjects, including assessment date, date of birth, country, age (in days), sex, ethnicity, race, length, and weight. Age (in days), sex, ethnicity, race, length, and weight will be summarized. The summary will include p-values (2-sided) from Fisher's exact test (for sex, ethnicity, and race) and Group t-test or Wilcoxon rank sum test (for age, length, and weight) comparing treatment groups.

9.3.2 Medical History and PPHN and Neonatal History

All significant past or ongoing medical conditions will be listed for all subjects. The listing will include the Medical Dictionary for Regulatory Activities (MedDRA) system organ class (SOC) and preferred term (PT) for each condition listed, and if the condition is ongoing at Baseline. These medical conditions will be summarized by PT within each SOC by treatment group and overall.

PPHN and neonatal history will be listed for all subjects. The listing will include current PPHN diagnosis; gestational age; birth weight; Appearance, Pulse, Grimace, Activity, Respiration (APGAR) scores at 1 and 5 minutes; and prior surfactant and prostaglandin therapy. Each of these assessments will also be summarized by treatment group and overall with appropriate summary statistics.

9.3.3 Concomitant Medications

All concomitant medications specified on the eCRF will be mapped to a standard name using the World Health Organization Drug Dictionary (WHO-DD).

The standard name and verbatim term of all concomitant medications will be listed for all subjects. This listing will include the date started (or indication that drug was ongoing at randomization), date discontinued (or indication that drug was ongoing at end of study), and the condition(s) treated/indication(s). If a subject received no medications, this will be indicated on

the listing. A summary of concomitant medications present at Baseline and a summary of concomitant medications added during the study will include the frequency and percentage of subjects in each treatment group receiving each drug (by coded standard name).

10 EFFICACY ANALYSES

Except where otherwise noted, all efficacy analyses will only be performed on the ITT population.

10.1 PRIMARY EFFICACY MEASURES

10.1.1 Primary Efficacy Analyses

10.1.1.1 Hypothesis

The primary efficacy endpoint of clinical worsening assesses if treprostinil reduces the incidence of clinical worsening through Day 14 over placebo in subjects with PPHN. The null and alternative hypotheses are:

$$H_0: p_1 = p_2$$

$$H_a: p_1 \neq p_2,$$

where p_1 and p_2 are the proportion of subjects who experience clinical worsening in the treprostinil and placebo treatment groups, respectively.

10.1.1.2 Primary Efficacy Analysis

The frequency and percentage of subjects who experience clinical worsening through Day 14 will be calculated for each treatment group. A chi-square test will be conducted to compare the incidence of clinical worsening between the treprostinil and placebo treatment groups.

The SAS Procedure FREQ will be used. The pseudo SAS statements are listed below:

```
proc freq;
  tables Treatment* Worsening / chisq;
run;
```

10.1.1.3 Sensitivity and Subgroup Analyses

To further support the robustness and assess the sensitivity of the primary efficacy analysis of clinical worsening through Day 14 (provided that the primary analysis yields significant results),

the above summary and chi-square test will be repeated using each of the following modifications (if data permit):

- The Per Protocol population will be used instead of the ITT population
- PPHN diagnosis (associated with unilateral CDH versus not associated with unilateral CDH)

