3.5 NUMBER OF SUBJECTS

Approximately 70 subjects will be randomized (1:1) to either receive treatment with Remodulin or placebo to provide 66 evaluable neonates. Enrollment will be closed once 66 evaluable subjects have been enrolled. No more than 32 subjects with a diagnosis of PPHN associated with CDH will be enrolled; these subjects will be evenly enrolled (1:1) into the Remodulin and placebo groups.

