5.2 RANDOMIZATION

An Interactive Web Response System (IWRS) will be utilized for the central randomization procedure. Subjects will be randomized in a ratio between active and placebo of 1:1. No more than 32 evaluable subjects with a diagnosis of PPHN associated with CDH will be enrolled; these subjects will be balanced between the treatment groups.

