5 SAMPLE SIZE CONSIDERATIONS

Based on the systematic review of use of nitric oxide for respiratory failure in infants by Finer and Barrington (2006), 57.9% (194/335) subjects in the control group had an outcome of death or requirement for ECMO (Finer 2006). In this study, assuming 60% of subjects in the placebo group and 30% of subjects in the Remodulin group with an outcome of death, requirement for ECMO, or need for additional PH therapy, we calculated that 66 subjects (33 subjects per treatment group) will have at least 80% power to show a significant difference in favor of Remodulin at alpha level 0.05 (1-sided test). Approximately 70 subjects are planned to be

randomized (1:1) to either receive treatment with Remodulin or placebo in addition to the standard of care.

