8 GENERAL CONSIDERATIONS FOR DATA ANALYSES

All the data collected in the electronic Case Report Form (eCRF) will be listed. In general, listings will be sorted by treatment group, subject number, and scheduled assessment (if applicable). Listings will include assessment date, assessment time (if available), study day, and all relevant data collected in the eCRFs. For data collected on a fixed schedule, the assessment identifier or the nominal time point will also be included on the listing. Repeat or redundant observations within an assessment window and observations that do not fall within any predefined assessment window (and will, therefore, be excluded from summaries) will be flagged in these listings. Subjects who are not to be included in the analysis population (eg, Safety population, Per Protocol population) will be flagged.

In general, the data will be summarized by scheduled assessment (if applicable) within each treatment group. For continuous variables, summary statistics will include the mean, standard deviation, median, minimum, and maximum. For summaries of non-normal data, interquartile range (lower quartile, upper quartile) may also be included. Minimums and maximums will be expressed using the level of precision in which the variable was collected. All other statistics will be rounded, using an additional decimal place than was collected. For discrete variables, summaries will include the frequency and percentage in each category. Percentages will be rounded to 1 decimal place. For all inferential analyses and descriptive comparisons, p-values will be rounded to 4 decimal places. Values less than 0.0001 will be denoted as <0.0001, and values greater than 0.9999 will be denoted as >0.9999 whenever practical. Categories of discrete variables will be ordered and labelled as they appear in the eCRF, and all categories represented on the eCRF will be included in summaries, even when they do not apply to any subjects in the study.

Unless otherwise specified, all statistical tests will be 2-sided at alpha level 0.05. All statistical calculations will be completed using the SAS® Version 9.4 or above.

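### The CDH subgroup analysis tests treatment separately within each subgroup and never compares the two effects, so its p-values cannot show whether the effect is consistent.

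*SAP*

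**What the plan says.** SAP 10.1.1.3 applies only if the primary analysis is significant. It states that "the above summary and chi-square test will be repeated using each of the following modifications (if data permit", and one of the two modifications listed is "PPHN diagnosis (associated with unilateral CDH versus not associated with unilateral CDH". The analysis being repeated is that of SAP 10.1.1.2: the number and percentage of infants worsening in each arm, and a treatment-by-worsening chi-square test. The section gives its purpose as backing up the robustness of the primary analysis and checking its sensitivity.

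On level and sidedness, SAP 8 states: "Unless otherwise specified, all statistical tests will be 2-sided at alpha level 0.05".

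On subgroup size, Protocol 5.2 sets a ceiling: "No more than 32 evaluable subjects with a diagnosis of PPHN associated with CDH will be enrolled". Protocol 3.5 adds that "these subjects will be evenly enrolled (1:1) into the Remodulin and placebo groups".

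Elsewhere, SAP 8.1 plans no covariates. SAP 8.2 allows analyses to be stratified by CDH but names no method. Neither document plans a treatment-by-CDH interaction test, an interval for a subgroup effect or for the difference between effects, or a rule for reading discordant subgroup results.

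**The concern.** Whether a treatment effect is consistent across two groups is a question about the difference between two effects. A p-value below 0.05 in one group and above it in the other does not answer it, because each p-value depends on that group's size and on chance as well as on its effect. Here each subgroup holds at most about half of a trial sized for one overall comparison, so each test is weak. The subgroup tests are run only when the overall test has succeeded, and that condition makes a split result more likely.

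CDH is the only subgroup the SAP names and the only diagnosis with its own enrolment ceiling and 1:1 balance, so its result will be looked for. A split result could be taken as a sign that the drug works in one diagnosis and not the other, when the data show nothing of the kind.

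**Working it through.** **Inputs.** Event rates, from SAP 5: "assuming 60% of subjects in the placebo group and 30% of subjects in the Remodulin group". Trial size, from the same section: "66 subjects (33 subjects per treatment group) will have at least 80% power". The planning level there is one-sided 0.05. From SAP 8: two-sided 0.05 for the analyses. From Protocol 3.5 and 5.2: at most 32 evaluable CDH infants, allocated 1:1. If the ceiling is reached, that is 16 CDH infants per arm and, out of 66, 34 non-CDH infants or 17 per arm. A filled ceiling is an assumption.

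**Reproducing the plan's own figure.** With a mean rate of 0.45 and one-sided 0.05,

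n per arm = [1.645·√(2·0.45·0.55) + 0.842·√(0.24 + 0.21)]² / 0.30² = (1.157 + 0.565)² / 0.09 ≈ 32.9, that is 33.

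Power at 33 per arm is 80.1%, which agrees with the SAP.

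**Power within each subgroup** (true rates 60% and 30%, two-sided 0.05). The normal approximation is Φ{[0.30 − 1.96·√(2·0.45·0.55/n)] / √(0.45/n)}.
- n = 16: (0.30 − 0.345)/0.168 = −0.27, about 39%.
- n = 17: (0.30 − 0.334)/0.163 = −0.21, about 42%.

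Exact enumeration of all binomial outcomes with the uncorrected chi-square test, counting significance in favour of Remodulin, gives 41% and 45%.

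**Without the condition on the primary test.** The subgroups are independent, so exactly one is significant with probability 0.411·0.550 + 0.589·0.450 = 0.491.

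**With the condition.** Exact enumeration of both subgroups together gives a pooled test significant at two-sided 0.05 in 73.6% of trials. The pooled test is significant and exactly one subgroup is significant in 44.4%, and 0.444/0.736 = 0.603. Both subgroups are significant in 25.2% of the trials that pass, and neither in 14.6%.

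**Sensitivity of the 60%.**

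| Setting (same effect in both subgroups) | Exactly one significant, given a significant primary test |
|---|---|
| 16 + 17 per arm, 60% vs 30% | 60% |
| 12 CDH + 21 non-CDH per arm | 61–62% |
| 8 CDH + 25 non-CDH per arm | 67% |
| Stopped at 40 subjects, 10 + 10 per arm | 64% |
| 16 + 17 per arm, 60% vs 25% | 54% |
| 16 + 17 per arm, 60% vs 20% | 45% (both significant: 50%) |
| 16 + 17 per arm, all tests one-sided 0.05 | 54% |

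**What a direct comparison would do** (16 + 17 per arm). With identical effects, after a significant primary test, a Wald test on the difference between the two risk differences is significant in 6.4% of trials. A Wald test on the difference in log odds ratios is significant in 4.1%. If 60% versus 30% holds in one subgroup and 60% in both arms of the other, power is about 27% for the risk-difference test and 19–21% for the log-odds-ratio test. The simple approximation for the risk difference, 0.30/√(0.45/16 + 0.48/17) = 1.26, gives about 24%.

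**Interval widths.**
- Risk difference in CDH infants: 1.96·√(0.45/16) = 0.33, so about ±33 points. Non-CDH is similar.
- Difference between the two risk differences: 1.96·√(0.45/16 + 0.45/17) = 0.46, so about ±46 points.

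**The case against.** The plan draws no subgroup conclusion from a within-subgroup p-value. It repeats the summary as well as the test, so all four worsening percentages will be on the page and both risk differences can be read off. With 16 + 17 infants per arm, when exactly one subgroup is significant after a significant primary test, both observed effects favour the drug in about 97% of trials. The analysis is conditional, runs only if data permit, and belongs to a Phase II trial whose aim is to explore. CDH is not an objective or endpoint, and the SAP's list of tables has no CDH table for worsening. An interaction test at this size would usually miss even an effect confined to one group.

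Most of this stands and limits the weight of the point. A reader might infer that the plan will usually report that the drug works in one diagnosis and not in the other. The documents do not support that: they state no such inference, and the displayed percentages would normally argue against it. A reader might also take 60% as the chance that any run of this trial gives a split result. It is conditional on a significant primary test and rests on the planning assumptions.

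What the objection leaves untouched is that the section's stated purpose is robustness, and the only inferential output it plans cannot assess consistency. Low interaction power is a reason to report an interval for the difference in effect. It does not make separate p-values informative.

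**Conclusion.** The concern holds as a weakness of method in a secondary analysis. Under an identical effect in both subgroups, subgroup power of 41% and 45% makes a split result the most frequent outcome after a significant primary test, at about 60%. This rests on 60% versus 30% in both subgroups, a filled CDH ceiling, two-sided 0.05, and reading the SAP bullet as one test per subgroup, which is natural but not spelled out. Fewer CDH infants generally raise the figure and larger effects lower it: at 60% versus 20%, both subgroups being significant becomes slightly more likely than a split. The primary result is not affected, and the analysis is conditional and optional, so this is a change to consider, not one the trial depends on.

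**What to change.** In SAP 10.1.1.3, keep the percentages per arm and replace the within-subgroup p-values with:

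- the risk difference and 95% CI in CDH infants and in non-CDH infants;
- the difference between the two risk differences with its 95% CI, and the interaction test on that same scale. If an odds-ratio scale is preferred, the interval and the test should both be on it.

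Add two sentences on interpretation: that no claim of a differing effect will be made from within-subgroup p-values, and that a non-significant interaction is not evidence of equal effects.

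The cost is one SAP paragraph and a few lines of code, with no new data and no design change. The drawback is that the results will look imprecise: about ±33 points per subgroup, and interaction power of about 20–27% if only one group benefits. That is the information a trial of this size holds on the question.
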